### **8.3.7 Adverse Events Based on Examinations and Tests**

The results from the CSP mandated laboratory tests and vital signs will be summarised in the CSR.

Deterioration as compared to baseline in protocol-mandated laboratory values, vital signs should therefore only be reported as AEs if they fulfil any of the SAE criteria, are the reason for discontinuation of treatment with the investigational product or are considered to be clinically relevant as judged by the Investigator (which may include but not limited to consideration as to whether treatment or non-planned visits were required or other action was taken with the study intervention, eg, dose adjustment or drug interruption).

If deterioration in a laboratory value/vital sign is associated with clinical signs and symptoms,

the sign or symptom will be reported as an AE and the associated laboratory result/vital sign will be considered as additional information. Wherever possible the reporting Investigator uses the clinical, rather than the laboratory term (eg, anaemia versus low haemoglobin value). In the absence of clinical signs or symptoms, clinically relevant deteriorations in non-mandated parameters should be reported as AE(s).

Any new or aggravated clinically relevant abnormal medical finding at a physical examination as compared with the baseline assessment will be reported as an AE unless unequivocally related to the disease under study.

### 8.3.8 Hy's Law

Cases where a participant shows elevations in liver biochemistry may require further evaluation and occurrences of AST or ALT  $\geq 3 \times$  ULN together with total bilirubin  $\geq 2 \times$  ULN may need to be reported as SAEs.

Where AST or ALT  $\geq 3 \times$  ULN together with TBL  $\geq 2 \times$  ULN occurs, where no other reason, other than the study intervention, can be found to explain the combination of increases, eg, elevated alkaline phosphatase indicating cholestasis, viral hepatitis, another drug should be evaluated. The elevation in transaminases must precede or be coincident with (ie, on the same day) the elevation in TBL, but there is no specified timeframe within which the elevations in transaminases and TBL must occur.

Please refer to [Appendix D](#) for further instruction on cases of increases in liver biochemistry and evaluation of HL.

### 8.3.9 Reporting of Serious Adverse Events

All SAEs must be reported whether or not considered causally related to the IMP. All SAEs will be recorded in the eCRF.

If any SAE occurs in the course of the study, Investigators or other site personnel will inform the appropriate AstraZeneca representatives within one day ie, immediately but **no later than 24 hours** of when he or she becomes aware of it.

The designated AstraZeneca representative will work with the Investigator to ensure that all the necessary information is provided to the AstraZeneca Patient Safety data entry site **within one calendar day** of initial receipt for fatal and life-threatening events **and within 5 calendar days** of initial receipt for all other SAEs.

For fatal or life-threatening AEs where important or relevant information is missing, active follow-up will be undertaken immediately. Investigators or other site personnel will inform AstraZeneca representatives of any follow-up information on a previously reported SAE within one calendar day, ie, immediately but **no later than 24 hours** of when he or she becomes aware of it.

Once the Investigators or other site personnel indicate an AE is serious in the EDC system, an automated email alert is sent to the designated AstraZeneca representative.

If the EDC system is not available, then the Investigator or other study site staff reports a SAE to the appropriate AstraZeneca representative by telephone.

The AstraZeneca representative will advise the Investigator/study site staff how to proceed.

For further guidance on the definition of a SAE, see [Appendix B](#).

The reference document for definition of expectedness/listedness is the AZD3152/AZD5156 Investigator's Brochure.

### **8.3.10    Pregnancy**

All pregnancies and outcomes of pregnancy should be reported to AstraZeneca except for:

- If the pregnancy is discovered before the study participant has received any study intervention
- Pregnancies in the partner of male participants

#### **8.3.10.1    Maternal Exposure**

The IMP should not be given to pregnant women.

Pregnancy itself is not regarded as an adverse event unless there is a suspicion that the investigational product under study may have interfered with the effectiveness of a contraceptive medication. Congenital anomalies/birth defects and spontaneous miscarriages should be reported and handled as SAEs. Elective abortions without complications should not be handled as AEs. The outcome of all pregnancies (spontaneous miscarriage, elective termination, ectopic pregnancy, normal birth or congenital anomaly/birth defect) should be followed up and documented even if the participant was discontinued from the study.

If any pregnancy occurs in the course of the study, then the Investigator or other site personnel informs the appropriate AstraZeneca representatives within **1 day**, ie, immediately but **no later than 24 hours** of when he or she becomes aware of it.

The designated AstraZeneca representative works with the Investigator to ensure that all relevant information is provided to the AstraZeneca Patient Safety data entry site **within 1 or 5 calendar days** for SAEs (see [Section 8.3.9](#)) and **within 30 days** for all other pregnancies.

The same timelines apply when outcome information is available.

The PREGREP module in the eCRF is used to report the pregnancy and the paper-based PREGOUT module is used to report the outcome of the pregnancy.

### **8.3.11    Medication Error, Drug Abuse, and Drug Misuse**

#### **8.3.11.1    Timelines**

If an event of medication error, drug abuse, **or** drug misuse occurs during the study, then the

Investigator or other site personnel informs the appropriate AstraZeneca representatives within **1 calendar day**, ie, immediately but **no later than 24 hours** of when they become aware of it.

The designated AstraZeneca representative works with the Investigator to ensure that all relevant information is completed within **1** (Initial Fatal/Life-Threatening or follow up Fatal/Life-Threatening) **or 5** (other serious initial and follow up) **calendar days** if there is an SAE associated with the event of medication error, drug abuse, or misuse (see Section 8.3.9) and **within 30 days** for all other medication errors.

#### 8.3.11.2 Medication Error

For the purposes of this clinical study a medication error is an **unintended** failure or mistake in the treatment process for an IMP or AstraZeneca NIMP that either causes harm to the participant or has the potential to cause harm to the participant.

The full definition and examples can be found in [Appendix BB 4](#).

#### 8.3.11.3 Drug Abuse

Drug abuse is the persistent or sporadic **intentional**, non-therapeutic excessive use of IMP or AstraZeneca NIMP for a perceived reward or desired non-therapeutic effect.

The full definition and examples can be found in [Appendix BB 4](#).

#### 8.3.11.4 Drug Misuse

Drug misuse is the **intentional** and inappropriate use (by a study participant) of IMP or AstraZeneca NIMP for medicinal purposes outside of the authorized product information, or for unauthorized IMPs or AstraZeneca NIMPs, outside the intended use as specified in the protocol and includes deliberate administration of the product by the wrong route.

The full definition and examples can be found in [Appendix BB 4](#).

In this study participants will receive investigational products administered IM in the anterolateral thigh on Day 1. All participants will be dosed at the site, they will receive study intervention directly from the unblinded pharmacist or designee, under medical supervision. The chance for drug abuse and drug misuse by participant is rare.

### 8.4 Overdose

For this study, any dose of study intervention (or dosing frequency) greater than what is specified in this protocol will be considered an overdose (see [Table 5](#)).

- An overdose with associated AEs is recorded as the AE diagnosis/symptoms on the relevant AE modules in the eCRF and on the Overdose eCRF module.
- An overdose without associated symptoms is only reported on the Overdose eCRF module.

If an overdose on an AstraZeneca study intervention occurs in the course of the study, the Investigator or other site personnel inform appropriate AstraZeneca representatives

immediately, but **no later than 24 hours** of when he or she becomes aware of it.

The designated AstraZeneca representative works with the Investigator to ensure that all relevant information is provided to the AstraZeneca Patient Safety data entry site **within one or 5 calendar days** for overdoses associated with an SAE (see section 8.3.8) and **within 30 days** for all other overdoses.

## 8.5 Human Biological Samples

Instructions for the collection and handling of biological samples for central assessment will be provided in the study specific laboratory manual. Samples should be stored in a secure storage space with adequate measures to protect confidentiality. For further details on Handling of Human Biological Samples see [Appendix C](#).

Samples will be stored for a maximum of 15 years from the date of the issue of a Clinical Study Report in line with consent and local requirements, after which they will be destroyed/repatriated.

### 8.5.1 CCI [REDACTED]

CCI [REDACTED]

### 8.5.2 SARS-CoV-2 Neutralizing Antibodies

Neutralizing antibody titers against SARS-CoV-2 will be evaluated using a validated live neutralization assay. Samples for the assessment of neutralizing antibody titers against SARS-CoV-2 should be collected per the SoAs (Section 1.3.1). At each visit 2 aliquots should be collected: main and back up.

### 8.5.3 CCI [REDACTED]

CCI [REDACTED]

### 8.5.4 Pharmacodynamics

Pharmacodynamics will not be evaluated.

### 8.5.5 Virologic Assessments

At Visit 1, a rapid test for SARS-CoV-2 antigens will be performed at the study sites to assess inclusion criteria, materials for the test will be provided by AstraZeneca. Sample collection and

assay procedure will be carried out according to the instructions enclosed in the commercial rapid test kit.

## 8.6 Optional Genomics Initiative Sample

Optional Genomics Initiative research is not applicable in this study.

## 8.7 Medical Resource Utilization and Health Economics

Medical Resource Utilization and Health Economics parameters are not evaluated in this study.

# 9 STATISTICAL CONSIDERATIONS

## 9.1 Statistical Hypotheses

The primary objective of the study is to evaluate the safety of AZD3152 compared with placebo. No formal statistical hypothesis was proposed, and the data presentation and analysis will be descriptive in its nature.

## 9.2 Sample Size Determination

The primary objective of the study is to evaluate the safety of AZD3152 compared with placebo. Corresponding primary endpoints to be examined:

- Occurrence of AEs collected throughout the study
- Occurrence of SAEs collected throughout the study
- Occurrence of MAAEs collected throughout the study
- Occurrence of AESIs collected throughout the study

Sample size determination is based on the probability-based approach for a single event. The probability of adverse event is  $p$ , therefore, the probability of no adverse event is  $(1 - p)$ .

The probability of no observations in  $n$  observations  $= (1 - p)^n$ , and this probability is equal to  $(1 - \text{power})$ . We need to solve an equation:  $(1 - p)^n = (1 - \text{power})$  which is equal to  $n * \log_{10}(1 - p) = \log_{10}(1 - \text{power})$ .

Solving for  $n$ , we get:  $n = \log_{10}(1 - \text{power}) / \log_{10}(1 - p)$

The choice of the **CC1 threshold of AE rates** was based on the data from PROVENT study (D8850C00002/NCT04625725). The study was performed in similar population. Safety information used for the calculation was collected during a minimum of 5-month safety follow-up in all participants and a median duration of follow-up was approximately 6 months, which is equal to the planned observation period in the current study, additional safety data (collected for the longer follow-up period) in the final study report for PROVENT study was quite similar to what is collected at 5-month safety follow-up. In PROVENT study the frequencies of **SAE** were low: **CC1** in mAb (EVUSHELD) group and **CC1** in placebo group. Percentages of subjects experienced at least one **AESI** (anaphylaxis and other severe hypersensitivity reactions

and reactions at the site of injection) were also low and comparable both in mAb and placebo groups **CCI** respectively). Therefore, **the lowest frequency among all categories of safety events in active therapy arm** (in participants in the EVUSHELD group) **was reported as CCI** For sample size calculation in local study the **CCI threshold of AE rates** was used as clinically justified, because it will be sufficient to detect the rarest important AEs (SAEs, AESIs) in AZD3152 arm.

If the target power for AZD3152 group would be 80%, the equation to solve is

**CCI**

The arm in which **cci** subjects will receive AZD3152 will allow for the recognition of AEs occurring at a frequency of **CCI** or higher with **CCI** power. With randomization at 3:1 ratio, we should include not less than 108 participants (**cci** subjects in AZD3152 group and **cci** in placebo group). Thus, with expectation that drop-out rate will be around 5%, we should randomize **116 participants cci subjects in AZD3152 arm and cci in placebo arm**).

### 9.3 Populations for Analyses

The following populations are defined:

**Table 8 Populations for Analysis**

Population/Analysis set	Description
Full analysis set (FAS)/ Safety analysis set	All randomized participants who received part or all of study intervention. Participants in the FAS will be classified according to the assigned treatment. The safety analysis set will include participants from the FAS but report participants according to the actual treatment received regardless of the assigned treatment.
SARS-CoV-2 neutralizing antibody analysis set	All participants in the FAS with baseline and post-dose antibody measurements (i.e. at least one post-dose antibody measurement with a measurable SARS-CoV-2 titer in serum). Participants will be classified according to the actual received treatment. Participants with protocol deviations that may interfere with generation or interpretation of an antibody response may be excluded or have data collected after the protocol deviations set to missing.

### 9.4 Statistical Analyses

The statistical analysis plan will be finalized before conducting an interim analysis based on data in 116 subjects during the follow-up period of 29 days after administration of study intervention.

This section contains all the main features of the proposed analysis of the primary and secondary endpoints and how issues encountered in the analysis will be managed. Given the exploratory nature of the study, the section provides more general principles and guidance for some variables.

#### **9.4.1 General Considerations**

Categorical variables will be presented as frequencies and proportions in percent. Continuous variables will be presented as means, geometric means (where applicable), standard deviations, geometric standard deviations (where applicable), medians, minimum and maximum, and quartiles (where applicable), with number of observations. When necessary, means and geometric means will be provided with two-sided 95% confidence intervals (CI). Treatment arms will be descriptively compared by corresponding variables.

The data and results of the analyses will be presented in the form of tables as well as listings, sorted by treatment arms and participant numbers. Methods of analysis will be outlined in detail in the Statistical Analysis Plan.

Validated SAS software version 9.4 or R statistical package version 4.2 or higher will be used for statistical analysis and reporting of the study data. The results of the analysis presented in the clinical study report will be validated according to the company's standard operating procedures.

#### **9.4.2 Endpoints**

##### **9.4.2.1 Primary Endpoint**

Primary safety endpoint includes AEs and SAEs, MAAEs, and AESIs collected throughout the study. Adverse events and SAEs will be coded using the most recent version of MedDRA and will be summarized by system organ class and preferred term and by severity and relationship to study intervention as judged by the Investigator.

Intercurrent events: treatment policy will be applied, i.e., all events collected will be included in the analysis.

Safety analysis set will be used for the analysis of this endpoint.

Number and proportion of participants with AEs, SAEs, MAAEs, and AESIs (occurring throughout the study period after study intervention administration) separately will be provided for each arm, and will be descriptively compared between arms.

##### **9.4.2.2 Secondary Endpoint(s)**

###### **Secondary endpoint: Titer for SARS-CoV-2 emerging dominant variant(s) nAbs.**

Corresponding endpoints are GMTs and GMFTs for SARS-CoV-2 emerging dominant variant(s) nAbs.

Intercurrent events: Participants who experience a protocol deviation that can interfere with an antibody response or violate adherence to the assigned dose, become infected, receive COVID-19 treatment or vaccination that can alter nAb levels will have data collected after the intercurrent event set to missing for analysis of this endpoint (i.e., while-on-treatment strategy is applied).

SARS-CoV-2 neutralizing antibody analysis set will be used for the analysis of this endpoint.

Descriptive statistics for the log-transformed titer will include the number of participants, GMT and GMFR, corresponding gSD, 95% CI, minimum, and maximum and summarized by treatment arm, visit and optionally by virus variant.

The dominant SARS-CoV-2 variants circulating during the study will be identified by the time of analysis.

Summary measures for nAb responses against the emerging dominant variant circulating during the course of the study will be presented as GMT and GMFR at each scheduled visit involving collection of the relevant biosamples.

GMT and GMFT will be descriptively compared between treatment arms.

**Secondary endpoint: incidence of a post-treatment symptomatic COVID-19 case** (negative RT-PCR at baseline to positive RT-PCR or positive antigen test at any time up to 6 months AND symptoms specified in the modified WHO definition of symptomatic COVID-19).

Intercurrent events: Participants who become unblinded to treatment assignment and/or take other non-investigational product(s) for COVID-19 prevention, in both cases prior to having met the criteria for the COVID-19 endpoint, will have data collected after the intercurrent event set to missing for analysis of this endpoint (i.e., while-on-treatment strategy is applied).

The numbers and percentages of symptomatic COVID-19 cases up to 6 months will be presented. Treatment arms will be descriptively compared by corresponding variables.

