### 3 OBJECTIVES AND ENDPOINTS

**Table 4 Objectives and Endpoints**

Objectives	Estimand Descriptions/Endpoints
Primary  To evaluate the safety of AZD3152 compared with placebo	Population: Safety analysis set Endpoints: 

• Occurrence of AEs collected throughout the study

• Occurrence of SAEs, MAAEs, and AESIs collected throughout the study

 Intercurrent events: Treatment policy will be applied, i.e., all events collected will be included in the analysis regardless of the presence and timing of intercurrent events. Summary measure: The number and proportion of subjects with AEs, SAEs, MAAEs, AESIs.
Secondary  To compare the nAb responses to the SARS-CoV-2 emerging dominant variant(s) of concern circulating during the course of the study in serum following AZD3152 or placebo administration	Population: SARS-CoV-2 nAb analysis set Endpoint: Titer for SARS-CoV-2 emerging dominant variant(s) nAbs Intercurrent events: Participants who experience a protocol deviation that can interfere with an antibody response or violate adherence to the assigned dose, become infected, receive COVID-19 treatment or vaccination that can alter nAb levels will have data collected after the intercurrent event set to missing for analysis of this endpoint (i.e., while-on-treatment strategy is applied). Summary measure: Geometric mean titer (GMT) and geometric mean fold rise (GMFRs) (from baseline value through Day 29 after the single IM dose) of SARS-CoV-2 nAbs. Descriptive statistics for the log-transformed titer will include the number of participants, GMT and GMFR, corresponding gSD, 95% CI, minimum, and maximum and summarized by treatment arm.
To compare the incidence of symptomatic COVID-19 cases in participants receiving study intervention. (efficacy)	Population: Full analysis set Endpoint: Incidence of a post-treatment symptomatic COVID-19 case (negative RT-PCR at baseline to positive RT-PCR or positive antigen test at any time up

Objectives	Estimand Descriptions/Endpoints
	CC1  

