3.2 Analysis Populations

The following populations are defined:

Table 1 Populations for Analysis

Population/Analysis set	Description
Screened Set	All participants who provided the Informed Consent
Full analysis set (FAS)/ Safety analysis set	All randomized participants who received part or all of study intervention. Participants in the FAS will be classified according to the assigned treatment. The safety analysis set will include participants from the FAS but report participants according to the actual treatment received regardless of the assigned treatment.
SARS-CoV-2 neutralizing antibody analysis set	All participants in the FAS with baseline and post-dose antibody measurements (i.e. at least one post-dose antibody measurement with a measurable SARS-CoV-2 titer in serum). Participants will be classified according to the actual received treatment. Participants with protocol deviations that may interfere with generation or interpretation of an antibody response may be excluded or have data collected after the protocol deviations set to missing.

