3.3.4 Multiplicity/Multiple Comparisons

All analyses will be performed in descriptive manner, no hypothesis testing will be performed.

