4.1.2.2 Presentation

The number of participants included in each analysis set will be reported by treatment arm. In addition, for each analysis set, the number of participants excluded, including the reasons, will be reported.

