4.2.2.2 Derivations

The geometric means will be calculated as the mean of the assay results after taking the logarithm transformation and then anti-logarithm transformation the mean to express results on the original scale. Two-sided 95% CIs will be obtained by taking log transforms of assay results, calculating the 95% CI with reference to Student's t-distribution, and then anti-logarithm transforming the confidence limits.

Geometric mean fold rises (GMFRs) will be reported and limited to participants with non-missing values at both time points.

Dealing with missing and undetectable results (<LLOQ and >ULOQ) described in Appendix C. Participants who experience an important protocol deviation that can interfere with an antibody response or violate adherence to the assigned dose, become infected, receive COVID-19 treatment or vaccination that can alter nAb levels will have data collected after the intercurrent event set to missing for analysis of this endpoint (i.e., while-on-treatment strategy is applied).

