4.2.2.3 Analysis

GMT and GMFRs, corresponding gSD, 2-sided 95% CIs, minimum and maximum will be presented for each visit by treatment arm in tables separately each dominant variant of SARS-CoV-2. Also box and whiskers plots (separately for each dominant variant) will be presented in the following manner: dots show geometric means, lines within boxes are medians, box bounds are quartiles and whiskers are minimums and maximums.

Also all data will be presented in listings.

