APPENDIX C MISSING DATA ON NEUTRALIZING ANTIBODIES

The analysis of GMTs will use the following imputation methods:

- Missing titer values will not be imputed.
- Titer values measured below the LLOQ will be imputed with half the LLOQ in summaries and analyses but will be listed as reported in the raw data listings.
- Titer values measured above the ULOQ will be imputed at the ULOQ value.

[figure not shown]

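### The objective to compare neutralizing-antibody responses has no pre-specified AZD3152/placebo ratio with a CI; name one, with a key visit and no test

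*Protocol*

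**What the plan says.** Protocol Table 4 words the secondary objective as a comparison: "To compare the nAb responses to the SARS-CoV-2 emerging dominant variant(s) of concern circulating during the course of the study", after AZD3152 or placebo. Protocol 9.4.2.2 lists GMT and GMFR with gSD and 95% CI by arm and visit, and ends with "GMT and GMFT will be descriptively compared between treatment arms".

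The SAP keeps to this. Section 4.2.2.3 states that "GMT and GMFRs, corresponding gSD, 2-sided 95% CIs, minimum and maximum will be presented for each visit by treatment arm", with box plots and listings. Section 4.2.2.2 bases the CIs on Student's t for log titers within an arm, and adds that "Geometric mean fold rises (GMFRs) will be reported and limited to participants with non-missing values at both time points". The only ratio defined (SAP 4.2.2.1) is post-dose over baseline within a participant. SAP 3.3.4 states that "All analyses will be performed in descriptive manner, no hypothesis testing will be performed".

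Three further provisions bear on the point:
- The nAb analysis set (SAP 3.2, Table 1) requires "at least one post-dose antibody measurement with a measurable SARS-CoV-2 titer in serum". The documents do not define *measurable*.
- SAP Appendix C states that "Titer values measured below the LLOQ will be imputed with half the LLOQ in summaries and analyses".
- The GMFR summary runs through Day 29 in Protocol Table 4 but through Day 181 in the SAP 4.2 table, while SAP Section 2 records no changes to the protocol's analyses.

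**The concern.** Two within-arm intervals are not an interval for the ratio between arms. The plan names neither the contrast that answers the objective nor the visit at which it is read, so both can be settled after the data are seen. Protocol 4.2 describes neutralizing activity as the standard surrogate for efficacy in this drug class. Protocol 2.1 says the study is legally required for marketing authorization in Russia. This contrast is therefore likely to carry much of the efficacy argument from 116 participants.

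Redaction does not explain the gap. The blacked-out endpoint text is exploratory; the secondary nAb sections can be read in full.

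**Working it through.** **Plan's own sizes.** Protocol 9.2 needs at least 108 participants at 3:1 and expects about 5% drop-out. 108/0.95 = 113.7, so 114, and the next multiple of 4 is 116. 116 × 3/4 = 87 and 116 × 1/4 = 29, as in the synopsis. This size was set for adverse events. The documents state no nAb precision, so there is none to reproduce.

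**Assumptions.** The documents give neither the SD of log10 titer nor the correlation r between baseline and post-dose titer. I take SD 0.6 (range 0.5 to 0.7), equal in both arms, and r = 0.3, 0.5, 0.7.

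**Step 1: can a reader rebuild the contrast?** Let s0, s1 and sd be the log SDs of baseline titer, post-dose titer and fold rise, all obtainable from the planned gSDs. Then cov = (s0² + s1² − sd²)/2 and slope = cov/s0².
- Example: s0 = s1 = 0.6 and sd = 0.6 give cov = (0.36 + 0.36 − 0.36)/2 = 0.18 and slope 0.18/0.36 = 0.5.
- With n and the means by arm, this yields the common-slope ANCOVA difference and its SE. In a simulated complete data set of 87 vs 29, the summaries and the participant-level model gave the same result (difference 1.3104 log10, SE 0.1061).
- With missing post-dose values the result is approximate.

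**Step 2: how much does the choice matter?** The 95% CI factor is 10^(t × SE × k), with SE = 0.6 × √(1/87 + 1/29) = 0.6 × 0.2144 = 0.1287 and t = 1.981 (114 or 113 df).

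| Contrast | k | r = 0.3 | r = 0.5 | r = 0.7 |
|---|---|---|---|---|
| Unadjusted GMT ratio | 1 | 1.80 | 1.80 | 1.80 |
| Ratio of GMFRs | √(2(1 − r)) | 2.00 | 1.80 | 1.58 |
| ANCOVA, common slope | √(1 − r²) | 1.75 | 1.66 | 1.52 |

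- Below r = 0.5 the GMFR ratio is less precise than the unadjusted ratio.
- At r = 0.5, SD 0.5 gives 1.63 unadjusted and 1.53 by ANCOVA; SD 0.7 gives 1.98 and 1.81.
- At 81 vs 27 and SD 0.6 the figures are 1.84 unadjusted and 1.79, 1.69, 1.54 by ANCOVA.
- If active-arm titers do not depend on baseline (r = 0 active; 0.3, 0.5, 0.7 placebo), the GMFR ratio gives 2.09, 1.94, 1.77. Simulated common-slope ANCOVA gives about 1.73 to 1.79, almost no gain over 1.80.
- With equal SDs, placebo supplies (1/29)/(1/29 + 1/87) = 75% of the variance, so the standard error should not rely on pooling if the SDs differ.

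**Step 3: which visit?** Protocol 4.1 allows vaccination after the Day 29 assessments. SAP 4.2.2.2 then sets later titers to missing where vaccination can alter them. Ratios after Day 29 may therefore rest on a selected subset.

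**Step 4: the *measurable* rule, only if it means at or above LLOQ.** I simulated 400,000 placebo participants with five post-dose visits, SD 0.6 and within-person correlation 0.8. A participant is dropped if all five values lie below LLOQ; other values below LLOQ are set to LLOQ/2.

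| Placebo samples below LLOQ | Placebo dropped | Of 29 | Placebo GMT raised |
|---|---|---|---|
| 5% | 1% | 0.3 | 1.03-fold |
| 10% | 3% | 0.8 | 1.07-fold |
| 20% | 7% | about 2 | 1.16-fold |
| 40% | 21% | 6.0 | 1.35-fold |

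Over correlation 0.7 to 0.9 the rise is 1.02 to 1.06 at 5% and 1.26 to 1.51 at 40%. If no active participant is dropped, the AZD3152/placebo ratio is divided by the same factor.

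**The case against.** The strongest reply is that the plan is descriptive by design. Protocol 9.1 states no hypothesis, SAP 3.3.4 rules out testing, and a side-by-side table is a comparison of a kind. The planned output is also rich enough to rebuild any of the three ratios, and the listings would let anyone holding them fit the model directly. The precision gain is modest, every SD and correlation is assumed, and a linear adjustment helps less if many baselines sit at LLOQ/2.

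Most of this stands. A reader might infer that the baseline-adjusted estimate is lost unless the SAP adds it. Step 1 shows that it is not. A reader might also infer that the plan breaks its own rules or states a wrong figure. It does neither.

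The descriptive design does not dispose of the point, though. It excludes tests, not estimates, and the plan already reports CIs without tests. Being able to rebuild three contrasts does not say which one answers the objective.

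On *measurable*, a reader might infer that placebo participants will be dropped and the ratio biased. The documents do not support that, because the word may simply mean a valid result, and then the issue disappears. Any loss would also be visible: SAP 4.1.2.2 says that "for each analysis set, the number of participants excluded, including the reasons, will be reported". Visibility would not correct the ratio.

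**Conclusion.** The gap is real but limited. An objective worded as a comparison has no named between-arm estimate, CI or key visit in the readable plan. This calls for an addition to a descriptive plan; no stated figure is wrong. The main gain is a contrast fixed in advance. The precision gain runs from almost none to a CI factor of 1.52 in place of 1.80, for 87 vs 29, SD 0.6 log10 and roughly normal, uncensored log titers. It may be smaller if many baselines lie below LLOQ. The *measurable* point is secondary and depends on one reading of an undefined word. Under that reading, selecting on the outcome raises the placebo GMT and pulls the ratio toward 1, slightly at 5% of placebo samples below LLOQ and materially at 40%.

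**What to change.** In SAP 4.2.2.3, for each dominant variant:
- Add the AZD3152/placebo GMT ratio with two-sided 95% CI from an ANCOVA of log titer on arm and log baseline titer, with unequal-variance or robust standard errors because of the 3:1 allocation.
- Fit it after the existing while-on-treatment rule, and show it without a p-value beside the GMT and GMFR tables.
- Name Day 29 as the key visit and the other visits as supportive. Reconcile the Day 29 wording in Protocol Table 4 with the Day 181 wording in the SAP 4.2 table.

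In SAP Table 1, define *measurable*. If it means at or above LLOQ, repeat the ratio in all dosed participants with a baseline and any post-dose sample, with values below LLOQ at LLOQ/2 as in Appendix C.

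Cost: one SAP paragraph, one model per variant and visit, and one conditional repeat. It needs no new samples, test or alpha, and the sample size is unchanged.
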